3.8. Randomisation

Randomisation will be undertaken by PHE Behavioural Insights Team. An up-to-date list of schools will be obtained from each area (or obtained from PHE and validated by the local team). Schools will be identified by their Unique Reference Number (School URN) to create the allocation list. Randomisation will be stratified by Provider and local authority. It is unlikely that we will know in advance (i.e. at the time of randomisation) which schools have email/SMS systems. (We anticipate this to be fairly common amongst schools.) We will therefore allocate all schools, irrespective of their available system, to one of the four trial arms. Randomisation will be carried out using a randomisation tool (e.g. ralloc or random number generator with schools ranked for allocation by random number order) in Stata, or other appropriate statistical-package to one of the four arms of the trial.

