Providers will obtain data on the implementation and fidelity of any reminder message delivered by the school (in line with the Standard Operating Procedure). For schools in trial arms 1 and 3 (who will be asked to send reminder messages to parents) providers will ascertain whether schools implemented the request to send a message to parents and if so, what medium they used (SMS and/or email) and whether they altered the message. For schools in trial arms 2 and 4 (who will not be explicitly asked to contact parents) providers will ascertain whether schools sent a message to parents (before or after the invitation letter but not including mention in newsletters or similar). We anticipate that providers will collect this information during the immunisation session at the school.

[figure not shown]
Finally, given the geographical and temporal variation in immunisation flu uptake levels and variation in the use of template letters in different areas, we will collect and analyse the letters sent in non-trial areas. This will give us valuable insight into the extent to which national templates are adopted and an understanding of the variation in invitation letters. This information will inform the understanding of the analysis of the trial, with respect to understanding changes in uptake seen from year to year in non-

^v Available at <https://www.compare-school-performance.service.gov.uk/download-data>

trial areas. To collect this information we will request that areas send us a copy of their invitation letter for this year's immunisation programme. This request will most likely be sent from NHS England central team ([name] and [name] – co-investigators on this trial) asking commissioners to obtain invitation letters from their local providers).

Figure 2. Data flow from allocation list, PHE National Infection Service immunisation data and school characteristics data, with linkage through the School Unique Reference Number (URN).

Abbreviations: NIS: National Infection Service; Pn Provider

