3.10. Data analysis

Analysis will be undertaken by the PHE Behavioural Insights Team working with the Statistic Unit, PHE National Infection Service. Our main analysis will be by intention to treat allocation for the primary and secondary outcomes. We will use logistic regression to investigate the main effect of the interventions and their interaction. The model also will include provider, local authority and school effect to take into account extra variation that was not explained by intervention and other confounder variables. In the models, we will also investigate the impact of secondary factors such as school-year (to determine if there's any greater impact for those that have not previously

received an invitation letter) and inequalities (e.g. IMD quintile, proportion of children eligible for free school meals, proportion of children not with English as first language).

We will also undertake a per-protocol analysis of the primary and secondary outcomes, including in the analysis only those schools in trial arms 1 and 3 who implemented the request to send a reminder message with high fidelity to the request and those schools in trial arms 2 and 4 who did not send a reminder request. While the intention to treat analysis will be a composite of the effectiveness of reminders and the prevalence of SMS/email systems, the per-protocol analysis will enable these components to be disentangled.

We will analyse the invitation letters used in non-trials areas by coding the letters using the Theoretical Domains Framework (TDF). This will enable us to assess their behavioural-insight framing and fidelity to the new template letter. We will analyse whether those areas that used a letter similar to the new template had i) higher uptake and ii) greater change in uptake from to last year, compared to areas that used a dissimilar letter.

4. Study sponsorship and approvals

This study has been reviewed by the PHE Research Ethics and Governance Group to gain approval for PHE to act as the study sponsor.

Health Research Authority (HRA) approval has been sought, which includes ethical (opinion provided through UK Health Departments' Research Ethics Service), governance and legal review. (HRA/ethics number xxxxxxxx).

The trial has been registered on clinicaltrials.gov, trial number xxx.

5. Main risks and mitigation

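### The per-protocol comparison of reminders is not protected by randomisation, so it cannot without a stated assumption separate reminder effectiveness from the prevalence of SMS/email systems

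*Combined protocol and SAP*

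**What the plan says.** Combined protocol and SAP, 3.8 Randomisation: the team does not expect to know beforehand which schools can send messages. "We will therefore allocate all schools, irrespective of their available system, to one of the four trial arms". Of such systems it says: "We anticipate this to be fairly common amongst schools".

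3.9 Data collection: for arms 1 and 3, "providers will ascertain whether schools implemented the request to send a message to parents", together with the medium and any alteration of the text. For arms 2 and 4, "providers will ascertain whether schools sent a message to parents (before or after the invitation letter but not including mention in newsletters or similar". Neither list includes whether the school has an SMS/email system.

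3.10 Data analysis: intention to treat is the main analysis. The per-protocol analysis is defined as "including in the analysis only those schools in trial arms 1 and 3 who implemented the request to send a reminder message with high fidelity", set against "those schools in trial arms 2 and 4 who did not send a reminder request". Intention to treat is described as mixing reminder effectiveness with system prevalence, and the section then says that "the per-protocol analysis will enable these components to be disentangled".

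**The concern.** The two sides of the per-protocol comparison pass through different filters, both applied after randomisation. A school with no system, or one that ignores the request, is removed if allocated to a reminder and retained if not. A school inclined to message parents unprompted is retained if allocated to a reminder and removed if not. Both filters tilt the reminder side towards schools that readily send.

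If those schools would have had different uptake anyway, the comparison mixes that difference with the effect of the reminder. The plan gives some reason to take this seriously: its background section reports that uptake varies with deprivation and ethnicity. Whether sending follows the same lines is not known from the documents.

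At stake is the only estimate the plan offers of how well reminders work where they are sent. Followed as written, the plan would report a selected comparison as that effect.

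**Working it through.** **Figure in the plan.** There is none for the per-protocol analysis. As a check on the inputs, row 1 of Table 5 (1 point, 90% power, ICC 0.025, cluster size 100; two-sided 5% assumed) gives 2 × (1.960 + 1.282)² × 16.2² ≈ 5,515 children per group. Multiplying by (1 + 99 × 0.025)/100 gives 192 clusters against 187 stated; SD 16.0 gives exactly 187. The point does not rest on this.

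**Inputs from the documents.** Table 4 lists 1,726 schools, so 863 per level of the reminder factor under equal allocation. Section 3.7 gives uptake 63.0%, SD 16.2 points, ICC 0.025 and 100 children per school. Reading 16.2 as the SD of school uptake is one option. The ICC implies a smaller value: 100 × √(0.025 × 0.63 × 0.37 + 0.975 × 0.63 × 0.37/100) = 9.0. Both are shown.

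**Assumed inputs.** c is the share of arm 1 and 3 schools that send as asked. s is the share of arm 2 and 4 schools that send unprompted. r is the correlation between uptake without a reminder and a latent propensity to send. An r of 0.1 corresponds to about 0.08 with actual sending at 60%, and about 0.06 at 10%. None of these is in the documents.

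**Bias with no true effect and no covariate adjustment.**
Bias = SD × r × [φ(z_c)/c + φ(z_s)/(1 − s)], where φ is the normal density at the cut-off for each share.
- c = 0.6, s = 0.1: 16.2 × 0.1 × (0.3863/0.6 + 0.1755/0.9) = 1.62 × 0.839 = 1.36
- c = 0.9, s = 0.05: 1.62 × (0.1755/0.9 + 0.1031/0.95) = 1.62 × 0.304 = 0.49

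SE = SD × √[1/(863c) + 1/(863(1 − s))], which is 0.92 at 60%/10% and 0.81 at 90%/5% (SD 16.2). The false-positive rate is Φ(bias/SE − 1.96) + Φ(−bias/SE − 1.96). SD cancels in bias/SE, so the rate is the same at both SDs.

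| c / s | r | Bias, SD 16.2 | Bias, SD 9.0 | False-positive rate |
|---|---|---|---|---|
| 60% / 10% | 0.05 | 0.68 | 0.38 | 11.5% |
| 60% / 10% | 0.1 | 1.36 | 0.76 | 31.5% |
| 80% / 10% | 0.1 | 0.88 | 0.49 | 18.1% |
| 90% / 5% | 0.05 | 0.25 | 0.14 | 6.1% |
| 90% / 5% | 0.1 | 0.49 | 0.27 | 9.3% |

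A negative r reverses the sign. If covariates explained half the variance in school uptake and the residual r stayed at 0.1, the 60%/10% bias would be multiplied by √0.5, giving 0.96 / 0.53.

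**Cross-check without the latent model.** If senders and non-senders differ by δ in underlying uptake, bias = (1 − c)δ + sδ. With c = 0.6, s = 0 and δ = 4 points, this is 1.6. In 4,000 simulated trials the per-protocol mean was 1.59 and it rejected in 42%; intention to treat averaged −0.01.

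**Complier analysis.** In 3,000 simulated trials at 60%/10%, r = 0.1, SD 16.2 and no effect, per-protocol averaged 1.38 (rejecting 32%) and the complier estimate 0.04 (rejecting 5%). With a true effect of 2 points, intention to treat gave 1.02, per-protocol 3.40 and complier 2.04.

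**The case against.** **Intention to treat is primary.** This stands. It is a reason to keep the point modest. A reader might infer that the trial's main conclusion on reminders is compromised; the documents do not support that.

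**Covariates are in the models.** Section 3.10 includes provider, local authority and school effects, mentions confounders in general terms, and looks at deprivation, free school meals and first language. Using the same models for the per-protocol set is the natural reading, although the text does not say so or choose covariates as predictors of sending. Adjustment could shrink the bias, and the table leaves it out.

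**The plan collects the data needed to judge the problem.** Largely right. It provides that "Providers will obtain data on the implementation and fidelity of any reminder message delivered by the school (in line with the Standard Operating Procedure", which should yield compliance and self-sending. A reader might infer that there is no way to tell whether the bias is large or small; that goes too far. Only the link between sending and underlying uptake is not directly observed, and the school characteristics in 3.9 would allow senders and non-senders to be compared. No such comparison is planned.

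**System availability may be recorded.** The Standard Operating Procedure is not among the documents. A reader might infer that system prevalence goes unrecorded, but the text supports only that 3.9 does not list it. On that text, lack of a system cannot be told apart from not complying.

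**The size is assumed, and the alternative is imprecise.** Both stand. With the 451 schools that 3.7 attributes to one provider, the 60%/10%, r = 0.1 false-positive rate falls from 31.5% to 11.8%, because the standard error grows. Complier power for 2 points would then be about 10% at SD 16.2.

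**Conclusion.** The concern holds, limited to the per-protocol analysis and the sentence that interprets it. The groups compared are not those randomised. Barring offsetting biases, separating effectiveness from availability requires sending to be unrelated to the uptake a school would have had without a reminder, given the model covariates. The condition is not that sending is unrelated to observed uptake: an effective reminder would itself create that relation.

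Under the assumed inputs (zero true effect, all 1,726 schools, no adjustment, r of 0.05 to 0.1, SD 9.0 to 16.2), bias is about 0.4 to 1.4 points with false-positive rates of 11.5% to 31.5% at 60%/10%. At 90%/5% it is about 0.1 to 0.5 points with rates of 6% to 9%. Table 5 works with 1 and 2 points, so the error could matter or could be minor. The expectation in 3.8 that systems are common points towards the smaller figures, though having a system is not the same as sending as asked. A reader might also infer that the per-protocol result must flatter reminders; the documents do not establish the direction.

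**What to change.** 1. In 3.10, replace the sentence on separating the components. Say that the per-protocol analysis is exploratory, is not protected by randomisation, and relies on sending being unrelated to the uptake expected without a reminder, given the covariates. Put the school characteristics from 3.9 in that model, and compare senders with non-senders on them.

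2. Add a supporting complier average causal effect analysis, with allocation to reminder as the instrument for any reminder sent. Adjust for provider, local authority and the letter factor, and weight by eligible children so that it matches the planned outcome. State its assumptions: allocation acts only through sending (a request might also prompt newsletter mentions, which 3.9 does not count), and no school sends only when not asked. State also that it estimates the effect of any message in complier schools, not of high-fidelity delivery.

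3. Use one definition of any reminder sent in all four arms. At the provider contact already planned in 3.9, ask every school whether it has an SMS/email system. This must be settled before the immunisation sessions, where the data are expected to be collected.

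**Cost.** Some wording, two standard questions and one model; randomisation, interventions and the main analysis do not change. The downside is precision. Complier SE = SD × √(4/1726)/(c − s). At SD 16.2 and a 50-point difference in sending this is 0.78/0.5 = 1.56, against 0.92 for per-protocol, with about 25% power for 2 points (64% at SD 9.0). At an 85-point difference it is 0.92, with 59% power (98% at SD 9.0). Total error is not always smaller: at 60%/10% and SD 16.2, root mean square error is 1.64 for per-protocol against 1.56 at r = 0.1, but 1.14 against 1.56 at r = 0.05. The complier analysis should therefore support the planned analyses, not replace them.

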In 2015/16 nationally, uptake in Years 1 and 2 was 53.6%.² Areas that participated in the pilot programme vaccinating primary school children (5-11 years) showed both decreasing uptake with increasing age (from 62.6% in Year 1 to 54.7% in Year 6 in 2015/16) and lower uptake last year than the previous year (57.9% compared with 60.4%). Delivery methods (school, GP or pharmacy) had considerable impact on uptake, with higher uptake in those areas that delivered flu immunisation through schoolsⁱ. Analysis has also shown that lower uptake is associated with deprivation and ethnicity.

The majority of areas offer the immunisation through school-based programmes delivered by providers that are commissioned by the NHS. Parents of eligible children are sent a letter informing them about the vaccination programme and inviting them to return the consent form for their child's vaccination. While uptake in schools is higher than GP or pharmacies, there remains approximately 30% of children for whom consent is neither given nor actively withheld.³

PHE provides template letters that immunisation providers can use. The PHE Behavioural Insights Team has worked with the NHS England and the PHE immunisation team to design the template letter for 2016/17. This letter is informed by behavioural insight theory to encourage parents to return the consent form.

There is evidence from the field of behavioural science to suggest that a low cost intervention, such as the content of an invitation letter or a reminder text message, may be effective in changing behaviour. In a previous trial run by our team, PHE Behavioural Insights Team, a 4% increase in health checks was shown by simplifying invitation letters and adding a tear-off slip where individuals could note the time and

ⁱ (55.6%, 32.9% and 16.1% uptake school, GP and pharmacy delivery respectively)

date of their first appointment, as a memory aid.⁴ Redesigning the invitation letter in combination with primer and reminder text messages increased uptake by 12% compared to the standard letter. Similar effects have been found in other non-health areas, for example, research from the Behavioural Insights Team and the DVLA showed that including an image of a person's car in their car tax collection letter increased tax payments from 40%-49%⁵ and an HMRC trial showed that providing a localised social norm message increased tax returns by 5%.⁶

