5.1. Timelines

The main risk to the successful implementation of this trial is meeting the timeline to enable local areas to implement the randomisation of letters component of the trial (mid-July deadline for most areas). The delay in initiating this development of the trial has been due to changes in budgets at PHE which led to a reduction and delay in the resources that could be allocated to this project. Should the trial not gain approvals in time to implement the randomisation of letters in a participating area, we will recommend that the area use the behaviour insights informed template letter for all

schools. Such areas would be invited to trial the effect of the SMS/email reminder on uptake. In the unlikely scenario of all areas being unable to participate in the letter-intervention (due to print-deadlines being ahead of approvals), the evaluation of the new template will rely on the ecological-analysis of fidelity to the new template letter in non-trial areas and uptake. While we are and will actively work with research sites to aim for this approach, if particular areas are unhappy to universally use the new template letter, we will take the above approach using the local letter updated from last year. One of the main reasons for including a large number of research sites at this stage is to give us the greatest possibility of running an effective and sufficiently powered trial, given the practical considerations.

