Appendix 1. Behavioural-insight framed letter

[Provider letterhead plus NHS logo]

**TEMPLATE LETTER FOR SCHOOL-AGED
CHILDREN**

[Date]

Dear Parent/Guardian,

Your child's annual flu vaccination is now due

This vaccination programme is in place to help protect your child against flu. Flu can be an unpleasant illness and sometimes causes serious complications. Vaccinating your child will also help protect more vulnerable friends and family by preventing the spread of flu.

Please complete the enclosed consent form (one for each child) and return to the school [by/ within] **[INSERT DATE or TIME FRAME]** to ensure your child receives their vaccination.

The vaccination is free and recommended for young children, and will be given by a quick and simple spray up the nose.

A leaflet explaining the vaccination programme is enclosed and includes details about the small number of children for whom the nasal vaccine is not appropriate.

Last year, most children offered the vaccine in schools had the immunisation.

If you have any queries please contact the healthcare team on [INSERT NUMBER].

Yours sincerely,

[Signed by Provider]

If your child becomes wheezy or has their asthma medication increased after you return this form, please contact the healthcare team on [phone number].

If you decide you do not want to vaccinate your child against flu, please return the consent form giving the reason. This will help us plan and improve the service.

For further information see: www.nhs.uk/child-flu

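### The non-trial-area comparison of letter similarity with uptake ignores delivery method, which alone could produce a difference as large as the effect of interest

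*Combined protocol and SAP*

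**What the plan says.** Section 3.9 has invitation letters collected from non-trial areas, with no criterion for how those areas deliver the vaccine. Section 3.10 has the letters coded with the Theoretical Domains Framework for behavioural framing and fidelity to the new template. It then sets two outcomes. The first is level: "We will analyse whether those areas that used a letter similar to the new template had i) higher uptake". The second is change: whether the similar-letter areas had "greater change in uptake from to last year, compared to areas that used a dissimilar letter". No restriction, stratification or adjustment is named for either outcome. For the randomised models, by contrast, the same section lists provider, local authority and school effects and several inequality measures.

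The background, before section 2, states: "Delivery methods (school, GP or pharmacy) had considerable impact on uptake". Its footnote i gives the figures: "55.6%, 32.9% and 16.1% uptake school, GP and pharmacy delivery respectively". It also says: "The majority of areas offer the immunisation through school-based programmes".

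The template in Appendix 1 is written for school delivery: "Please complete the enclosed consent form (one for each child) and return to the school".

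Section 5.1 gives the comparison a fallback role. If no area can take part in the letter randomisation, "the evaluation of the new template will rely on the ecological-analysis of fidelity to the new template letter in non-trial areas and uptake".

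**The concern.** Delivery method is linked to uptake on the protocol's own figures, and it is plausibly linked to letter similarity. An area that vaccinates through GPs or pharmacies could hardly use the return-to-school instruction as it stands, and the template's social-norm sentence also refers to schools. Such areas would therefore tend to score lower on fidelity. If they collect in the dissimilar group, the crude uptake comparison credits the letter with a difference that belongs to delivery method.

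What is at stake is the reading of a supplementary analysis in the expected case, and the whole evaluation of the letter in the fallback case.

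**Working it through.** The plan gives no sample size, power or effect estimate for this comparison, so there is no planned figure to reproduce.

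**Inputs**
- Uptake by delivery method: school 55.6%, GP 32.9%, pharmacy 16.1% (background, footnote i; season not stated).
- National uptake in Years 1 and 2, 2015/16: 53.6% (background).
- Uptake in pilot areas, 2015/16: 62.6% in Year 1, 54.7% in Year 6 (background).
- Effect of interest: 1 point (63% to 64%), or 2 points in the other rows of Table 5 (section 3.7). These were set for the randomised trial and serve here only as a yardstick.
- Share of non-school areas in each letter group: not given, so assumed and varied.

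**Step 1. Gaps.** School minus GP = 55.6 − 32.9 = 22.7 points. School minus pharmacy = 55.6 − 16.1 = 39.5 points.

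**Step 2. Spurious difference in outcome (i) with no letter effect.** Let p_D and p_S be the non-school shares of the dissimilar and similar groups. Then the similar-minus-dissimilar difference = gap × (p_D − p_S). With p_S = 0:

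| p_D (assumed) | All GP | All pharmacy |
|---|---|---|
| 5% | 0.05 × 22.7 = 1.1 | 0.05 × 39.5 = 2.0 |
| 20% | 0.20 × 22.7 = 4.5 | 0.20 × 39.5 = 7.9 |

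If p_D = p_S the difference is 0. If p_S exceeds p_D the sign reverses.

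**Step 3. Imbalance needed to match the effect of interest.** For GP delivery, 1/22.7 = 4.4% gives 1 point and 2/22.7 = 8.8% gives 2 points. For pharmacy delivery the shares are 1/39.5 = 2.5% and 2/39.5 = 5.1%.

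**Step 4. Is such a share plausible?** Assume that the footnote and the 53.6% describe the same children and season. The implied non-school share of children nationally is then (55.6 − 53.6)/22.7 = 8.8% if all GP, or (55.6 − 53.6)/39.5 = 5.1% if all pharmacy. If all of these children are in dissimilar-letter areas, and those areas hold a fraction q of all children, the spurious difference is 2.0/q: 2.2 points at q = 0.9, 4.0 at q = 0.5 and 6.7 at q = 0.3.

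**Step 5. Outcome (ii), change from last year.** A stable gap between delivery methods cancels in a year-on-year change. What remains is a change of method in an area, a different trend by method, or a difference in the year groups compared. On the last, Table 1 adds Year 3 nationally in 2016/17, while former pilot areas already covered Years 1 to 6. The pilot-area age slope is (62.6 − 54.7)/5 = 1.58 points per school year. Moving from Years 1–2 (mean year 1.5) to Years 1–3 (mean year 2.0) lowers average uptake by 0.5 × 1.58 = 0.79 point where Year 3 is new. The resulting bias is 0.79 × (difference between letter groups in the proportion of areas where Year 3 is new), which is zero if that proportion is equal.

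**The case against.** The strongest reply is that the size of the bias is unknown. Most areas deliver through schools. The documents do not say how many non-trial areas do not, whether those areas send a letter at all, or how it would be coded. Return-to-school is one feature among many in Table 2, alongside length, highlighting, the NHS logo and gain and loss framing. Provider type does not settle the matter either: section 3.5 and Table 4 list a pharmacy company among the providers of school vaccination. All of this stands, and it is why the result is conditional. It does not remove the concern, because Step 3 shows that an imbalance of a few per cent is enough.

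A reader might infer more than the documents support:
- *That the comparison would mainly measure delivery method.* That needs a non-school share and a coding pattern that the documents do not give.
- *That GP and pharmacy areas have lower uptake because of delivery alone.* The footnote figures are unadjusted, and the background also ties uptake to deprivation and ethnicity.
- *That outcome (ii) fails in the same way.* It removes stable differences between methods.
- *That the 0.79-point Year 3 shift is itself a bias.* It applies to both letter groups wherever Year 3 is new. Table 1 lists only six continuing pilot areas in 2015/16, and the notes to section 3.2 place some of the pilot areas among the trial sites.
- *That any missed print deadline leaves this as the only evidence on the letter.* Section 5.1 says so only if every area is unable to randomise letters, which it regards as unlikely.

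**Conclusion.** The concern holds in conditional form. As written, outcome (i) can show an advantage for the template of 1.1 to 4.5 points when there is none, if 5% to 20% of dissimilar-letter areas deliver by GP and no similar-letter area does. That is comparable to or larger than the 1 to 2 points of interest, and pharmacy delivery would make it larger. Both the shares and the coding pattern are assumptions, and with an even spread the bias is zero. Outcome (ii) is affected only through the three routes in Step 5.

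The randomised comparison is untouched. The point is worth correcting because the confounder is one that the protocol itself identifies, and because in the fallback nothing else would evaluate the letter.

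**What to change.** Amend sections 3.9 and 3.10 before the uptake data are seen:
1. Record delivery method for each non-trial area when its letter is requested.
2. Restrict the comparison to school-delivered non-trial areas, or stratify by delivery method. Either sets the between-method component to zero.
3. Calculate year-on-year change in the year groups offered in both seasons in each area. Section 3.9 says that data are routinely submitted by school year, so this is feasible.
4. Adjust for deprivation using the IMD measure already planned in section 3.9.
5. Label the raw uptake comparison as descriptive.

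The cost is protocol wording, one extra field in the letter request and a filter at analysis. IMD is planned by school postcode, so it would need summarising to area level, and extending to non-trial schools if the planned linkage covers only trial schools. The main downside is fewer areas in the comparison. Change in the common year groups also leaves out Year 3 where it is new, so that group could be reported separately as uptake only.
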